1.0 Introduction

This Statistical Analysis Plan (SAP) describes the statistical analyses for OnabotA X Study M21-324 Glabellar Lines: Safety and Efficacy of OnabotulinumtoxinA X in Subjects with Glabellar Lines.

Study M21-324 examines the efficacy and safety of OnabotA X in female subjects with severe glabellar lines.

The SAP will not be updated in case of administrative changes or amendments to the protocol unless the changes impact the analysis.

Unless noted otherwise, all analyses will be performed using SAS Version 9.4 (SAS Institute Inc., Cary, NC 27513) or later under the Linux operating system.

2.0 Study Design and Objectives

2.1 Objectives, Hypotheses and Estimands

The primary objective of the study is to evaluate the safety of OnabotA X injection in the glabellar region of female subjects with severe GL.

[figure not shown]
The clinical hypothesis is that OnabotA X has an acceptable safety profile when administered to the corrugator and procerus muscles in subjects with severe GL.

No estimand is defined for the safety evaluations.

2.2 Study Design Overview

The schematic of the study is shown in Figure 1.

Figure 1. Study Schematic

2.3 Treatment Assignment and Blinding

Subjects will be randomized to Formulation A, Formulation B, or Formulation C, each in combination with standard of care, in a 1:1:1 ratio. AbbVie will provide instructions for OnabotA X Formulations A, B, and C admixture preparations and treatment administration separately, in the pharmacy manual.

[figure not shown]
2.4 Sample Size Determination

A sample size of 90 (30 per treatment group) subjects will provide sufficient data for safety evaluations of OnabotA X to support future placebo-controlled studies in larger sample sizes, powered for efficacy evaluations.

3.0 Endpoints

3.1 Primary Endpoint(s)

Not applicable.

3.2 Secondary Endpoint(s)

Not applicable.

3.3 Other Efficacy Endpoint(s)

All efficacy endpoints will utilize the Facial Wrinkle Scale for Glabellar Lines (FWS-GL) and/or the Allergan Glabellar Line Severity Scale (AGLSS), each of which are scored on a 0-3 range, where 0 = None, 1 = Mild, 2 = Moderate, and 3 = Severe.

[figure not shown]
The efficacy endpoints for the investigator-rated and subject-rated FWS-GL at maximum frown include:

- Number and proportion of subjects who achieve 1-grade improvement from baseline;
- Number and proportion of subjects who achieve 2-grade improvement from baseline;
- Number and proportion of subjects who achieve 2-grade improvement from baseline in both Investigator and Subject ratings;
- Number and proportion of subjects who achieve a "None" or "Mild" rating

With the exception of the endpoint above that is based on both the Investigator and Subject ratings, the other endpoints listed above are calculated separately for Investigator-rated and subject-rated FWS-GL.

The efficacy endpoints for the Allergan Glabellar Line Severity Scale (AGLSS) at maximum frown evaluated by independent investigator (separate from the investigator evaluating FWS-GL) include:

- Number and proportion of subjects rated at least "Mild" at baseline who achieve 1-grade improvement from baseline;
- Number and proportion of subjects rated at least "Moderate" at baseline who achieve 2-grade improvement from baseline;

• Number and proportion of subjects at least "Moderate" at baseline who achieve a "None" or "Mild" rating

The efficacy endpoints for the subjects whose glabellar lines were rated at least "Mild" at baseline at rest include:

- Number and proportion of subjects with 1-grade improvement from baseline in investigator-rated FWS-GL;
- Number and proportion of subjects with 1-grade improvement from baseline in FWS- subject-rated GL;
- Number and proportion of subjects who achieve a 1-grade improvement from baseline in AGLSS

The FWS-GL endpoints will be assessed at screening, baseline, and at each follow-up visit, while the AGLSS endpoints will only be assessed at baseline and Day 30.

[figure not shown]
3.4 Safety Endpoint(s)

The safety endpoints for this study include:

- Adverse Events
- Abbreviated Physical Examination (general appearance, head, ears, eyes, nose, throat, and neck)
- Clinical Laboratory Test (hematology, chemistry, and urinalysis)
- Vital Sign Measurements (body temperature, pulse rate, respiration rate, systolic and diastolic blood pressure)
- Electrocardiogram (heart rate, QRS duration, QT interval, QTcB interval, QTcF interval, ST segment, RR interval, PR interval)
- Neurologic Assessment

3.5 Additional Endpoint(s)

The following additional endpoints will also be assessed:

Immunogenicity: Blood samples for immunogenicity testing will be collected from all subjects treated with OnabotA X at Day 1 (Baseline), Day 30, Day 90, and End-of-Study (Day 180). Collected samples will be processed to yield serum for detection of binding and neutralizing antibodies to OnabotulinumtoxinA.

Hypersensitivity: Blood samples are to be collected within 2 hours of suspected anaphylaxis or systemic hypersensitivity reaction.

4.0 Analysis Populations

The following population sets will be used for the analyses.

The Full Analysis Set (FAS) includes all randomized subjects who received at least 1 dose of study drug. The FAS will be used for all efficacy and baseline analyses. Subjects in this population will be analyzed per randomization, regardless of actual treatment received.

[figure not shown]
The Safety Analysis Set consists of all subjects who received at least 1 dose of study drug. The Safety Analysis Set will be used for all safety analyses. Due to the difficulty of determining the actual treatment received if wrong kits are given or reconstitution is not done correctly, subjects in this population will be analyzed per randomization.

5.0 Subject Disposition

The total number of subjects who were screened, enrolled, and treated will be summarized. Reasons for exclusion, including screen failure, will be summarized.

A summary of subject accountability will be provided where the number of subjects in each of the following categories will be summarized for each treatment group:

- Subjects enrolled (randomized) in the study;
- Subjects who were treated;
- Subjects who completed the study;
- Subjects who prematurely discontinued (all reasons and primary reason);

• Subjects in each analysis population, as applicable.

For end of study participation, the number and percentage of subjects who completed the protocol defined follow-up period (or did not with associated reasons) will be summarized overall and by treatment group.

6.0 Study Drug Duration and Compliance

Duration of exposure will be summarized with descriptive statistics (mean and standard deviation, median, Q1, Q3, minimum, and maximum). The number of subjects exposed for specific period of time (1-30 days, 31-60 days, 61-90 days, 91-120 days, 121-150 days, 151-180 days, and >180 days) will also be summarized. Duration of exposure will be calculated as date of study exit minus date of study drug administration +1.

7.0 Demographics, Baseline Characteristics, Medical History, and Prior/Concomitant Medications

Demographics, baseline characteristics, medical history, prior and concomitant medications, and concurrent procedure will be summarized overall and by treatment group for the FAS. Categorical variables will be summarized with the number and percentage of subjects; percentages will be calculated based on the number of non-missing observations. Continuous variables will be summarized with descriptive statistics (number of non-missing observations, mean and standard deviation, median, minimum, and maximum).

7.1 Demographics and Baseline Characteristics

Continuous demographic variables include age. Categorical demographic variables include sex, ethnicity, race, age group (18-25, 26-40, 41-55, 56-64, or \geq 65 years).

Baseline characteristics include weight, height, body mass index (BMI), Fitzpatrick skin type, baseline Investigator-rated and subject-rated FWS-GL severity at maximum frown and rest, and baseline AGLSS severity at maximum frown and at rest.

7.2 Medical History

Medical history data will be coded using the Medical Dictionary for Regulatory Activities (MedDRA). The actual version of the MedDRA coding dictionary will be noted in the statistical tables and clinical study report. The number and percentage of subjects in each medical history category (by MedDRA system organ class and preferred term) will be summarized overall and by treatment group. The system organ class (SOC) will be presented in alphabetical order, and the preferred terms will be presented in alphabetical order within each SOC. Subjects reporting more than one condition/diagnosis will be counted only once in each row (SOC or preferred term).

7.3 Prior and Concomitant Medications

[figure not shown]
Prior and concomitant medications will be summarized by generic name. A prior medication is defined as any medication taken prior to the date of the first dose of study drug. A concomitant medication is defined as any medication that started prior to the date of study drug administration and continued to be taken after the first dose of study drug or any medication that started on or after the date of the first dose of study drug. The number and percentage of subjects taking medications will be summarized by generic drug name based on the World Health Organization (WHO) Drug Dictionary for both prior and concomitant medications.

7.4 Concurrent Procedure

All procedures undergone on or after Study Day 1 visit through the exit visit will be considered concurrent procedures. Concurrent procedure will be summarized by MedDRA high-level term and preferred term. The MedDRA high level term will be presented in alphabetical order, and the preferred terms will be presented in alphabetical order within each high-level term. A listing will be generated for concurrent procedures.

8.0 Handling of Potential Intercurrent Events for the Primary and Key Secondary Endpoints

Not applicable.

9.0 Efficacy Analyses

9.1 General Considerations

Data will be summarized for subjects for the FAS Population. For the efficacy analyses, subjects are summarized based on the randomized treatment assigned.

The number and percentage (or proportion) of the subjects who are responders will be summarized. Calculation of a 95% CI with an exact method based on the binomial distribution will be utilized alongside the summary data.

"Baseline" refers to the last non-missing observation before the first administration of study drug or randomization if no study drug is given.

9.2 Handling of Missing Data

Missing data will not be imputed. Instead, the following method will be used for the efficacy summary data:

• As Observed (AO): The AO analysis will not impute values for missing evaluations, and thus a subject who does not have an evaluation on a scheduled visit (within the applicable visit window) will be excluded from the AO analysis for that visit. AO will include all values collected in the study.

[figure not shown]
9.3 Primary Efficacy Endpoint(s) and Analyses

9.3.1 Primary Efficacy Endpoint(s)

Not applicable.

9.3.2 Main Analysis of Primary Efficacy Endpoint(s)

Not applicable.

9.3.3 Sensitivity and Supplementary Analyses of the Primary Efficacy Endpoint(s)

Not applicable.

9.4 Secondary Efficacy Endpoints and Analyses

9.4.1 Key Secondary Efficacy Endpoints

Not applicable.

9.4.2 Main Analyses of Key Secondary Efficacy Endpoints

Not applicable.

9.4.3 Sensitivity and Supplementary Analyses for Key Secondary Efficacy Endpoints

Not applicable.

[figure not shown]
9.4.4 Supportive Secondary Efficacy Endpoints and Analyses

Not applicable.

9.5 Additional Efficacy Analyses

Additional Efficacy Endpoints are:

- Achievement of ≥1-grade improvement from baseline on the investigator-rated FWS-GL at maximum frown by visit
- Achievement of ≥1-grade improvement from baseline on the subject-rated FWS-GL at maximum frown by visit
- Achievement of ≥2-grade improvement from baseline on the investigator-rated FWS-GL at maximum frown by visit
- Achievement of ≥2-grade improvement from baseline on the subject-rated FWS-GL at maximum frown by visit

- Achievement of None or Mild on the investigator-rated FWS-GL at maximum frown by visit
- Achievement of None or Mild on the subject-rated FWS-GL at maximum frown by visit
- Achievement of ≥2-grade improvement from baseline on both the investigatorrated and subject-rated FWS-GL at maximum frown by visit
- Achievement of ≥1-grade improvement from baseline on the AGLSS at maximum frown for those who were rated at least Mild at baseline
- Achievement of ≥2-grade improvement from baseline on the AGLSS at maximum frown for those who were rated at least Moderate at baseline
- Achievement of None or Mild on the AGLSS at maximum frown for those who were rated at least Moderate at baseline
- Achievement of ≥1-grade improvement from baseline on the investigator-rated FWS-GL at rest by visit for those who were rated at least Mild at baseline
- Achievement of ≥1-grade improvement from baseline on the subject-rated FWS-GL at rest by visit for those who were rated at least Mild at baseline
- Achievement of ≥1-grade improvement from baseline on the AGLSS at rest for those who were rated at least Mild at baseline

Listings of all endpoint values for each subject will also be provided.

9.6 Efficacy Subgroup Analyses

[figure not shown]
Not applicable.

10.0 Safety Analyses

10.1 General Considerations

Safety data will be summarized for the Safety Analysis Set. For the safety analyses, subjects are summarized based on the treatment as randomized.

For safety analyses, "Baseline" refers to the last non-missing observation before the first administration of study drug unless otherwise noted.

10.2 Adverse Events

Adverse events (AEs) will be summarized overall and by treatment group and presented using primary MedDRA System Organ Classes (SOCs) and preferred terms (PTs) according to the version of the MedDRA coding dictionary used for the study at the time of database lock. The actual version of the MedDRA coding dictionary used will be noted in the AE tables and in the clinical study report. Specific adverse events will be counted once for each subject for calculating percentages, unless stated otherwise. In addition, if the same adverse event occurs multiple times within a subject, the highest severity and level of relationship to investigational product will be reported.

[figure not shown]
10.2.1 Treatment-Emergent Adverse Events

Treatment-emergent AEs are defined as any AE with the onset that is after the study drug administration. Events where the onset date is the same as the study drug start date are assumed to be treatment-emergent. All treatment-emergent AEs will be summarized overall, as well as by primary MedDRA SOC and Preferred Term. The SOCs will be presented in alphabetical order, and the PTs will be presented in alphabetical order within each SOC.

10.2.2 Adverse Event Overview

An overview of AEs will be presented consisting of the number and percentage of subjects experiencing at least one event for each of the following AE categories:

- Any treatment-emergent AE
- Any treatment-emergent AE related to study treatment according to the investigator
 - Any treatment-emergent AE related to study procedure according to the investigator
 - Any treatment-emergent AE related to study drug according to the investigator
- Any severe treatment-emergent AE

- Any severe treatment-emergent AE related to study treatment according to the investigator
- Any serious treatment-emergent AE
 - Any serious treatment-emergent AE related to study treatment according to the investigator
- Any treatment-emergent AE leading to death
- Any treatment-emergent PDSOT AEs
- All deaths

10.2.3 Treatment-Emergent Adverse Events by SOC and/or PT

Treatment-emergent adverse events will be summarized by SOC and PT; by maximum severity and SOC and PT; and by subject number and SOC and PT. Specific adverse events will be counted once for each subject for calculating percentages, unless stated otherwise. In addition, if the same adverse event occurs multiple times within a subject, the highest severity and level of relationship to investigational product will be reported.

[figure not shown]
In addition, treatment-emergent adverse events will be summarized by PT and sorted by decreasing frequency for the overall group. Treatment-related treatment-emergent adverse events, study drug related treatment-emergent adverse events, and study procedure related treatment-emergent adverse events will also be summarized by SOC and PT.

10.2.4 SAEs (Including Deaths) and Adverse Events Leading to Study Drug Discontinuation

SAEs (including deaths) will be summarized by SOC and PT and in listing format.

10.2.5 Potential Distant Spread of Toxin Adverse Events

To assess PDSOT, MedDRA preferred terms that may be associated with botulinum toxin effects have been identified (Appendix B). All TEAEs associated with PDSOT will be tabulated by PT; in addition, all PDSOT TEAEs will be listed by subject.

10.3 Analysis of Laboratory Data

[figure not shown]
Data collected from central and local laboratories, including additional laboratory testing due to an SAE, will be used in all analyses, except for Baseline where SAE-related laboratory assessments before the first dose of study drug will be excluded. The clinical laboratory tests defined in the protocol operations manual (e.g., hematology, clinical chemistry, and urinalysis) will be summarized by treatment group.

Each laboratory variable will be summarized for all time points (starting with Baseline) with the number of non-missing observations, mean and standard deviation, median, minimum and maximum. Mean change from baseline to each applicable post-baseline visit will be summarized for selected laboratory variables, with the number of observations, baseline mean, and visit mean. The change from baseline mean, standard error, and 95% confidence interval will be presented for the mean change from baseline within each treatment group.

Changes in laboratory parameters will be tabulated using shift tables categorized as low, normal, or high based on the normal ranges of the laboratory used for each sample. A shift table from baseline to the minimum post-baseline value, to the maximum post-baseline value, and to the final post-baseline value will be created.

Laboratory abnormalities will be evaluated based on Potentially Clinically Important (PCI) criteria (Table C-1 in Appendix C). For each laboratory PCI criterion, the number and percentage of subjects who have a post-baseline laboratory value meeting the criteria will be summarized. The percentages will be calculated relative to the number of participants with at least 1 postbaseline assessment. The numerator will be the total number of participants with at least 1 PCI postbaseline value during the study that is more extreme than baseline (if present).

Listings will be provided to summarize subject-level laboratory data for subjects meeting PCI criteria.

A listing of possible Hy's Law cases, defined as those who meet all of the following conditions simultaneously, will be provided: ALT > $3 \times ULN$ or AST > $3 \times ULN$ that is associated with an increase in bilirubin $\geq 2 \times ULN$ and alkaline phosphatase $< 2 \times ULN$.

[figure not shown]

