Appendix C. Potentially Clinically Important Criteria for Safety Endpoints

Table C-1. Criteria for Potentially Clinically Important Clinical Laboratory Values

		Criteria ^a				
Parameter	Flag	Observed Value				
Hema	Hematology					
Hemoglobin (g/L)	High	Increase in >2 g/dL above ULN or > baseline if baseline >ULN				
	Low	<100				
WDC Count (1000/L)	High	-				
WBC Count (10^9/L)	Low	< 3				
Neutrophils (10^9/L)	High	-				
Neutrophilis (10 9/L)	Low	<1.5				
Lampaha antas (1000/L)	High	>4				
Lymphocytes (10^9/L)	Low	<0.8				
Plotoleta (1000/L)	High	-				
Platelets (10^9/L)	Low	<75.0				
International normalized ratio (INR)	High	>1.5 x ULN; >1.5 times above baseline if on anticoagulation				
	Low	Not Applicable				
Chen	nistry					
Albumin (g/L)	High	-				
Albumin (g/L)	Low	<30				
Alkaline Phosphatase (U/L)	High	>2.5 x ULN				
Alkainie Phosphatase (O/L)	Low	-				
A1	High	>3.0 x ULN				
Alanine Aminotransferase (U/L)	Low	-				
Associate Assistant Fance (IVI)	High	>3.0 x ULN				
Aspartate Aminotransferase (U/L)	Low	-				

Table C-1. Criteria for Potentially Clinically Important Clinical Laboratory Values (Continued)

		Criteria ^a
Parameter	Flag	Observed Value
T.4.1 D'l' -1 '- (1/I)	High	>1.5 x ULN
Total Bilirubin (umol/L)	Low	-
Calairen (nemal/L)	High	Corrected serum calcium >2.9@; Ionized calcium >1.5
Calcium (mmol/L)	Low	Corrected serum calcium <2.0@; Ionized calcium <1.0
Cholesterol (mmol/L)	High	>10.34
Cholesterol (minor/L)	Low	-
Creatining (surge)/I)	High	>1.5 x ULN
Creatinine (umol/L)	Low	-
Commo Clutomy I Tropoforoso (I./I.)	High	>2.5 x ULN
Gamma Glutamyl Transferase (U/L)	Low	-
Character (normal/L)	High	>13.9
Glucose (mmol/L)	Low	<2.2
Potassium (mmol/L)	High	>5.5
Potassium (mmor L)	Low	<lln< td=""></lln<>
Sodium (mmol/L)	High	>150
Soutum (mmor)	Low	<130
Trickycorides (mmol/L)	High	>5.70
Triglycerides (mmol/L)	Low	-
Phosphate (mmol/L)	High	-
Thosphate (minor L)	Low	<0.8

a. A post-baseline value must be more extreme than baseline (if present) to be considered a potentially clinically important finding.

Note: LLN = Lower Limit of Normal; ULN = Upper Limit of Normal

[@] Calcium corrected for Albumin (can be used if it is confirmed with the lab that the result has been corrected for Albumin and not a different protein).

The criteria for PCI criteria for vital sign findings are described in Table C-2.

Table C-2. Criteria for Potentially Clinically Important Vital Sign Values

Cı		eria ^a	
Parameter	Flag	Observed Value	Change from Baseline

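### The listing of possible Hy's Law cases requires all criteria to be met at once, with no time window defined, so a subject whose bilirubin rises on a later draw than the transaminases can go unlisted

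*SAP*

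**What the plan says.** SAP Section 10.3 provides a listing of possible Hy's Law cases, "defined as those who meet all of the following conditions simultaneously". The conditions are ALT >3×ULN or AST >3×ULN, "that is associated with an increase in bilirubin" to at least 2×ULN, and alkaline phosphatase below 2×ULN. The section gives no time window and no rule for a missing result.

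The same section fixes the data that feed the listing: "Data collected from central and local laboratories, including additional laboratory testing due to an SAE, will be used in all analyses", with one exception that concerns baseline only.

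It also plans a second output: "Listings will be provided to summarize subject-level laboratory data for subjects meeting PCI criteria". Table C-1 in Appendix C sets the PCI limits analyte by analyte: ALT >3.0×ULN, AST >3.0×ULN, total bilirubin >1.5×ULN, alkaline phosphatase >2.5×ULN. A footnote adds a condition: "A post-baseline value must be more extreme than baseline (if present) to be considered a potentially clinically important finding".

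**The concern.** A listing of possible cases is a screen. It should catch candidates for medical review, and the review then rules them in or out. Bilirubin can rise after the transaminases have peaked, so the two criteria may be met on different draws in the same episode. A rule that needs them together can miss that pattern.

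The wording is also not fixed tightly enough to program. The sentence asks for simultaneity and then uses the looser idea of association. Two programmers could reasonably choose same sample, same date or same visit, and produce different listings from the same data.

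Safety is the primary objective (Section 2.1), and Section 2.4 justifies the sample size on safety grounds alone: "A sample size of 90 (30 per treatment group) subjects will provide sufficient data for safety evaluations". An empty Hy's Law listing could be carried forward to the larger studies as reassurance, so the rule behind it should be sensitive and unambiguous.

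**Working it through.** The SAP gives no figure to reproduce here. The check applies the Section 10.3 rule to constructed laboratory profiles.

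**Assumptions.** Simultaneous is read as the same draw. A missing value is taken as not meeting its condition. The SAP states neither.

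**Rules compared.**
- Present rule: some single draw has (ALT >3 or AST >3) and bilirubin ≥2 and alkaline phosphatase <2, all in multiples of ULN.
- Any-time rule: (ALT >3 or AST >3) on some post-baseline draw, and bilirubin ≥2 on some post-baseline draw.
- PCI (Table C-1): ALT >3.0, AST >3.0, bilirubin >1.5, each judged alone.

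**Worked example** (illustrative values; AST at or below 3×ULN and alkaline phosphatase normal on both draws).
- Draw 1: ALT 6, bilirubin 1.3. 6 > 3 is met; 1.3 ≥ 2 is not. The draw fails.
- Draw 2, a week later: ALT 2.8, bilirubin 2.6. 2.8 > 3 is not met; 2.6 ≥ 2 is. The draw fails.
- Present rule: not listed.
- Any-time rule: 6 > 3 and 2.6 ≥ 2, so listed.
- PCI: ALT qualifies on draw 1 (6 > 3.0) and bilirubin on draw 2 (2.6 > 1.5). Both values are flagged, provided they exceed baseline, but no criterion joins them.

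**Other profiles.**

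| Profile | Present rule | Any-time rule | Analytes meeting a PCI limit |
|---|---|---|---|
| All criteria met on one draw | listed | listed | ALT, AST, bilirubin |
| Transaminases and bilirubin met on different draws | not listed | listed | ALT, AST, bilirubin |
| Alkaline phosphatase missing | not listed | listed | ALT, AST, bilirubin |
| Bilirubin missing | not listed | not listed | ALT, AST |
| Only ALT missing, AST >3×ULN | listed | listed | AST, bilirubin |
| Only AST missing, ALT >3×ULN | listed | listed | ALT, bilirubin |

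The two rules differ in two rows: different draws, and missing alkaline phosphatase. In both, the single values cross PCI limits but carry no Hy's Law flag. A normal alkaline phosphatase, which the present rule requires, never meets a PCI limit itself.

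**The case against.** The strongest reply is that the information is not lost. A subject like the worked example would normally appear in the PCI listings for both ALT and bilirubin. If the extra draws were prompted by an SAE, the subject would be in the SAE listing too. The SAP does not give the layout of the PCI listings, and a subject-level layout might place the values side by side. This largely stands, and it is why the point is small. It does not remove the point, because no PCI criterion combines the analytes, and the Hy's Law listing exists to do that.

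A second reply is that the any-time rule trades specificity for sensitivity. Blood is sampled as late as Day 180 (Section 3.5, for immunogenicity), so unrelated elevations far apart could be paired. That is true, but dated values make the gap visible, and flagging those who meet the present rule keeps the narrower group identifiable.

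Some stronger readings are tempting but not supported:
- A reader might infer that any missing analyte removes a subject. It does not: ALT or AST alone suffices. Exclusion for missing alkaline phosphatase or bilirubin is inferred from the wording, since no missing-value rule is stated.
- A reader might infer from the use of local and SAE-driven tests that partial or closely spaced panels will occur. Section 10.3 says only that such data are used; incomplete panels are possible, not documented.
- A reader might attach a rate or confidence limit to an empty listing. The SAP plans a listing only, with no proportion or interval.

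**Conclusion.** The point holds as a cheap improvement. The timing condition is undefined. On its plain same-draw reading, it leaves out a subject whose bilirubin and transaminase criteria are met on different draws, and apparently one with no alkaline phosphatase result on the qualifying draw. The effect is a missing joint flag in one safety listing. No sample size, power or error rate is affected.

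The conclusion rests on reading simultaneous as the same draw and on treating a missing alkaline phosphatase as not below 2×ULN. If the sponsor intended a wider window, the omission shrinks, but the window still has to be written down. Expected numbers among 90 subjects are very small, and the SAP gives no rate from which to estimate them.

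**What to change.** Reword the listing in Section 10.3 as follows:
- Include every subject with any post-baseline ALT or AST >3×ULN and any post-baseline total bilirubin ≥2×ULN, whether or not on the same draw.
- For each, show all ALT, AST, bilirubin and alkaline phosphatase values with sample date and laboratory, so that the gap between elevations can be seen.
- Flag the subjects who also meet the present simultaneous rule, and state what simultaneous means for that flag.
- Do not exclude a subject because alkaline phosphatase is missing.

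For post-baseline values, every subject caught by the present rule is also caught by this one, so nothing now planned is lost. A subject whose bilirubin was never measured remains unlisted under either rule.

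The cost is a change of SAP wording and a slightly longer listing from data already collected. A few subjects with unrelated elevations far apart in time, or with alkaline phosphatase at or above 2×ULN, may be listed without the flag and ruled out on medical review.
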